5.3 LIFESTYLE CONSIDERATIONS

Lifestyle considerations are similar to patients treated with metastatic ALK+ NSCLC in other settings. Patients should contact their physicians immediately if they develop new or worsening neurologic symptoms or side effects suspected to be related to brigatinib therapy.

5.4 SCREEN FAILURES

Patients who have signed informed consent and subsequently fail to meet the inclusion and/or exclusion criteria are defined as screen failures. Once the investigator determines that screening will not continue for a patient, and the patient will not be enrolled in the study, the screen failure should be documented. Patients who screen fail may later be re-screened with prior sponsor-investigator approval.

5.5 STRATEGIES FOR RECRUITMENT AND RETENTION

Patient and physician interest in enrollment is expected to be high given the strong clinical rationale to support a strategy of brigatinib alone with close clinical and MRI surveillance as a potential strategy to avoid the toxicity of CNS RT. We anticipate that retention rates will be high given that the follow-up requirements are similar to the standard of care with the exception of the 1-week clinic visit and 3-week clinic visit and brain MRI. These additional follow up requirements are considered appropriate to ensure the safety of the brigatinib alone approach. All other clinic visits and follow up MRIs are considered to be consistent with the standard-of-care.

6 STUDY INTERVENTION

6.1 STUDY INTERVENTION(S) ADMINISTRATION

6.1.1 STUDY INTERVENTION DESCRIPTION

All patients will be started on brigatinib 90 mg daily for 7 days, before escalating to 180 mg daily thereafter.

The clinical follow-up and imaging requirements are similar to the standard of care with the exception of the 1-week clinic visit and 3-week clinic visit and brain MRI. These additional follow-up requirements are considered appropriate to ensure the safety of the brigatinib alone approach.

Patients who develop CNS progression will be treated with standard of care CNS RT, as prescribed by a board-certified radiation oncologist. CNS RT may entail stereotactic radiosurgery (SRS), WBRT, or partial brain radiotherapy, as appropriate in the opinion of the radiation oncologist. For guidance on radiation techniques and doses, adherence to the NCCN CNS tumor guidelines for brain metastases section (www.nccn.org) is recommended.

6.1.2 DOSING AND ADMINISTRATION

The recommended dosing regimen for brigatinib is 90 mg orally once daily for the first 7 days. If 90 mg is tolerated per investigator during the first 7 days, increase the dose to 180 mg orally once daily.

If brigatinib is interrupted for 14 days or longer for reasons other than adverse reactions, resume treatment at 90 mg once daily for 7 days before increasing to the previously tolerated dose. Interruptions due to treatment related AEs should be managed as per section 6.1.2.2 and 6.1.2.3 below.

Brigatinib may be taken with or without food. Instruct patients to swallow tablets whole. Do not crush or chew tablets. If a dose of brigatinib is missed or vomiting occurs after taking a dose, do not administer an additional dose and take the next dose of brigatinib at the scheduled time.

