6.1.2.1 RECOMMENDED BRIGATINIB DOSE REDUCTION LEVELS

Table 1: Recommended Brigatinib Dose Reduction Levels

Starting Dose	Dose Reduction Levels				
	First	Second	Third	Fourth	Fifth
90mg QD	60mg QD	Permanently discontinue	Not applicable	Not applicable	Not applicable
180mg QD	120mg QD	90mg QD	60mg QD	Permanently discontinue	Not applicable

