6.1.2.2 DOSE MODIFICATIONS FOR PNEUMONITIS

Pneumonitis and interstitial lung disease are known side effects of TKIs used in NSCLC, generally occurring later in the course of therapy. Crizotinib has been associated with severe, life-threatening, or fatal treatment-related pneumonitis in clinical trials with a frequency of 4 in 255 (1.6%) patients. Other TKIs used in the treatment of NSCLC have similar adverse reactions. In the ALTA trial, brigatinib was associated with pneumonitis in 3.7% of patients in the 90 mg group (90 mg once daily) and 9.1% of patients in the 90 → 180 mg group (180 mg once daily with 7-day lead-in at 90 mg once daily). Adverse reactions consistent with possible ILD/pneumonitis occurred early (within 9 days of initiation of brigatinib; median onset was 2 days) in 6.4% of patients, with Grade 3 to 4 reactions occurring in 2.7%.

Drug-related pneumonitis may be associated with signs and symptoms such as dyspnea, hypoxia, cough, hemoptysis, and fever as well as radiologic evidence of parenchymal or interstitial changes. The diagnosis of pneumonitis and determination of causal relationship to the drug is

often confounded by the underlying disease (especially lymphangitic carcinomatosis) and other factors such as lung infection and radiation effect due to non-specific signs and symptoms as well as similar radiological appearance. Pneumonitis should be suspected when such signs and symptoms develop or in asymptomatic patients when a new ground glass opacity or interstitial infiltration is noted in imaging studies. If a patient is considered to have the potential diagnosis of drug-related pneumonitis, physical examination, assessment of oxygen saturation, evaluation for infectious etiologies, and thoracentesis, bronchoscopy, or open lung biopsy should be considered to reach a diagnosis. If the causality is at least possibly related to the study drug, management of pneumonitis, including dose interruption and potential discontinuation, as presented in during first 7 days of treatment prior to escalation to 180 mg QD) and after escalation to 180 mg QD), is required.

BRIGATINIB DOSE MODIFICATION RECOMMENDATIONS FOR TREATMENT-RELATED PNEUMONITIS OCCURRING PRIOR TO DOSE ESCALATION TO 180 MG QD (IE, FIRST 7 DAYS OF TREATMENT):

Toxicity Grade (CTCAE v4.03)	Recommended Action

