Grade 1	Withhold the dose until pneumonitis returns to grade 0 (baseline), then resume at 90 mg and do not escalate. If pneumonitis recurs, permanently discontinue treatment.*
Grade 2	Withhold the dose until pneumonitis returns to Grade 0, then resume at 60 mg and do not escalate.* If pneumonitis recurs, permanently discontinue treatment.*
Grade 3	Permanently discontinue treatment.*
Grade 4	Permanently discontinue treatment.*

*Or in select cases per investigator discretion and discussion with Lead PI, consider continued use/shallower dose escalation as per Camidge et al, JTO 2019

BRIGATINIB DOSE MODIFICATION RECOMMENDATIONS FOR TREATMENT-RELATED PNEUMONITIS OCCURRING AFTER DOSE ESCALATION TO 180 MG QD:

Toxicity Grade (CTCAE v4.03)	Recommended Action
Grade 1	Withhold the dose until pneumonitis returns to grade 0 (baseline), then resume at the same dose. If pneumonitis recurs, permanently discontinue treatment.*
Grade 2	Withhold the dose until pneumonitis returns to Grade 0. Resume at 120 mg QD.* If pneumonitis recurs, permanently discontinue treatment.*
Grade 3	Permanently discontinue treatment.*
Grade 4	Permanently discontinue treatment.*

*Or in select cases per investigator discretion and discussion with Lead PI, consider continued use/shallower dose escalation as per Camidge et al, JTO 2019

6.1.2.3 DOSE MODIFICATION RECOMMENDATION TABLE FOR TREATMENT-RELATED ADVERSE EVENTS (EXCLUDING PNEUMONITIS)

Table 2: Brigatinib Dose Modification Recommendations for Treatment-Related Adverse Events (excluding pneumonitis)

Adverse Reaction	Severity*	Dose Modification
Hypertension	Grade 3 hypertension (SBP greater than or equal to 160 mmHg or DBP greater than or equal to 100 mmHg, medical intervention indicated, more than one anti-hypertensive drug, or more intensive therapy than previously used indicated)	
Withhold brigatinib until hypertension has recovered to Grade 1 or less (SBP less than 140 mmHg and DBP less than 90 mmHg), then resume brigatinib at same dose.Recurrence: withhold brigatinib until recovery to Grade 1 or less, and resume at next lower dose (Table 1) or permanently discontinue treatment.

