	Grade 4 hypertension (life-threatening consequences, urgent intervention indicated)	
Withhold brigatinib until recovery to Grade 1 or less (SBP less than 140 mmHg and DBP less than 90 mmHg), and resume at next lower dose (Table 1) or permanently discontinue treatment.Recurrence of Grade 4 hypertension: permanently discontinue brigatinib.
Bradycardia (HR less than 60 bpm)	Symptomatic bradycardia	
Withhold brigatinib until recovery to asymptomatic bradycardia or to a resting heart rate of 60 bpm or above.If a concomitant medication known to cause bradycardia is identified and

Adverse Reaction	Severity*	Dose Modification
		
discontinued or dose-adjusted, resume brigatinib at same dose upon recovery to asymptomatic bradycardia or to resting heart rate of 60 bpm or above.
 
• If no concomitant medication known to cause bradycardia is identified, or if contributing concomitant medications are not discontinued or dose-adjusted, resume brigatinib at next lower dose (Table 1) upon recovery to asymptomatic bradycardia or to resting heart rate of 60 bpm or above.
	Bradycardia with life-threatening consequences, urgent intervention indicated	
• Permanently discontinue brigatinib if no contributing concomitant medication is identified.• If contributing concomitant medication is identified and discontinued or dose-adjusted, resume brigatinib at next lower dose (Table 1) upon recovery to asymptomatic bradycardia or to a resting heart rate of 60 bpm or above, with frequent monitoring as clinically indicated.• Recurrence: permanently discontinue brigatinib.
Visual Disturbance	Grade 2 or 3 visual disturbance	Withhold brigatinib until recovery to Grade 1 or baseline, then resume at the next lower dose (Table 1)

Adverse Reaction	Severity*	Dose Modification
	Grade 4 visual disturbance	Permanently discontinue brigatinib
Creatine Phosphokinase (CPK) Elevation	Grade 3 CPK elevation (greater than $5.0 \times$ ULN)	
Withhold brigatinib until recovery to Grade 1 or less (less than or equal to $2.5 \times$ ULN) or to baseline, then resume brigatinib at same dose.If Grade 3 elevation of CPK recurs, brigatinib should be withheld until recovery to Grade 1 or less (less than or equal to $2.5 \times$ ULN) or to baseline, then resume at the next lower dose level per Table 1.

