6.2.2 FORMULATION, APPEARANCE, PACKAGING, AND LABELING

Brigatinib drug product is supplied as film-coated tablets containing 30 mg of brigatinib active pharmaceutical ingredient. Other ingredients are typical pharmaceutical excipients (lactose monohydrate, microcrystalline cellulose, sodium starch glycolate, colloidal silica, and magnesium stearate). The tablet coating is composed of typical pharmaceutical grade coating components (talc, polyethylene glycol, polyvinyl alcohol, and titanium dioxide). The drug product is

manufactured under current Good Manufacturing Practice in accordance with approved procedures. Brigatinib will be supplied in white high-density polyethylene bottles with induction sealed caps or blister packs. Bottle or blister pack labels will bear the appropriate label text as required by governing regulatory agencies. At a minimum, such text will include product name, product strength, number of tablets, and lot number.

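### The restart rule after a long interruption not caused by toxicity gives no workable dose for a patient maintained on 60 mg

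*Combined protocol and SAP*

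**What the plan says.** Section 6.1.2 gives a single restart rule for interruptions of 14 days or more. When the cause is not toxicity, the instruction is, "for reasons other than adverse reactions, resume treatment at 90 mg once daily for 7 days before increasing to the previously tolerated dose". The next sentence deals with the other case: "Interruptions due to treatment related AEs should be managed as per section 6.1.2.2 and 6.1.2.3 below".

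Section 6.1.2.1 ("Table 1: Recommended Brigatinib Dose Reduction Levels") makes 60 mg daily a permitted dose on both rows. It is the first reduction from 90 mg and the third from 180 mg.

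Two later sections can place a patient on 60 mg:

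- Section 6.1.2.2, Grade 2 pneumonitis before escalation to 180 mg: "Withhold the dose until pneumonitis returns to Grade 0, then resume at 60 mg and do not escalate". A footnote to that row adds: "Or in select cases per investigator discretion and discussion with Lead PI, consider continued use/shallower dose escalation".
- Section 6.1.2.3, Table 2, Grade 2 or 3 visual disturbance: "Withhold brigatinib until recovery to Grade 1 or baseline, then resume at the next lower dose (Table 1"). For a patient taking 90 mg, the next lower level is 60 mg.

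**The concern.** Patients reach 60 mg because a higher dose was not tolerated. The restart rule was evidently written with the usual 180 mg patient in mind, for whom a week at 90 mg is a cautious lead-in. For a 60 mg patient the same week is a rise above the tolerated dose, with no safety reason for it. On the 90 mg row of Table 1 and in the pre-escalation pneumonitis table, 90 mg is the very dose at which the toxicity occurred.

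What is at stake is the safety of a few individual patients and consistent dosing across the three sites. The 13-week disease control analysis is not at stake.

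**Working it through.** The plan states no figure on this point, so there is nothing to reproduce. The check applies the rule to each dose at which a patient can be maintained and then looks for text that supplies an exception.

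**Inputs.** Restart dose 90 mg for 7 days (Section 6.1.2); dose levels 60, 90, 120 and 180 mg (Table 1, Section 6.1.2.1); tablet strength 30 mg (Section 6.2.2); planned enrolment 23 (Section 9.2) and maximum 35, which also allows for screen failures (Section 1.1); early pneumonitis rates from Section 6.1.2.2.

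**Step 1: the rule at each level.** Step after the lead-in = previous dose − 90 mg.

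| Previous dose | Restart dose | Step after 7 days |
|---|---|---|
| 180 mg | 90 mg | +90 mg |
| 120 mg | 90 mg | +30 mg |
| 90 mg | 90 mg | 0 |
| 60 mg | 90 mg | −30 mg |

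The rule fails only at 60 mg, where the increase it calls for is a decrease.

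**Step 2: the excess at 60 mg under the literal reading.** 90 × 7 = 630 mg (21 tablets) against 60 × 7 = 420 mg (14 tablets). The excess is 210 mg over the week, and 90/60 = 1.5.

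**Step 3: the narrow reading.** If the word for a dose increase is taken to limit the rule to patients previously above 90 mg, the 60 mg patient falls outside it. No other section then gives a restart dose.

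**Step 4: does other text close the gap?**

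- The sentence on treatment-related events depends on the cause of the current interruption. A patient reduced earlier for toxicity who later stops for an unrelated reason is still under the restart rule.
- The ban on escalation covers only one route to 60 mg, Grade 2 pneumonitis before escalation. The restart rule does not refer to it, so for those patients two instructions conflict.
- Other routes carry no such ban. At 90 mg, one Grade 2 or 3 visual disturbance leads to 60 mg. So does a first Grade 4 rise in CPK, lipase or amylase (Table 2, Section 6.1.2.3).

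**Step 5: how often.** The documents give neither the share of patients who reach 60 mg nor the share with an interruption of 14 days or more for other reasons. For one expected affected patient, the product of the two shares would have to be 1/23 = 4.3% at planned enrolment, or 1/35 = 2.9% at the maximum.

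Only the early pneumonitis route has a stated rate. Section 6.1.2.2 reports it "in 6.4% of patients, with Grade 3 to 4 reactions occurring in 2.7" percent. Assuming one denominator, Grade 1–2 is 6.4% − 2.7% = 3.7%. That is 0.037 × 23 = 0.851 patients, or 0.037 × 35 = 1.295. The interruption shares below are assumed for illustration; they are not in the documents.

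| Assumed share with a later non-toxicity interruption | Expected of 23 | Expected of 35 |
|---|---|---|
| 5% | 0.04 | 0.06 |
| 10% | 0.09 | 0.13 |
| 20% | 0.17 | 0.26 |

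One expected patient by this route would need an interruption share of 1/1.295 = 77% with 35 patients. With 23 it would need 1/0.851 = 118%, which is impossible. These counts are too high for this route, because Grade 1 cases resume at 90 mg and because the 6.4% covers onset within 9 days while the table covers the first 7. They do not bound the whole trial, since the other routes have no stated rate.

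**The case against.** The strongest reply is that the literal reading defeats the sentence's own verb. No sensible investigator would take a patient already reduced to 60 mg up to 90 mg and call the return to 60 mg an increase. On the natural reading the protocol is silent about a rare case and does not instruct an overdose, and the 1.5-fold figure disappears.

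The riskiest route also has its own restriction. Section 6.1.2.2 calls its pneumonitis management required once causality is at least possible, and a specific restriction would reasonably prevail over a general restart sentence. Pneumonitis after escalation does not lead directly to 60 mg: Grade 2 resumes at 120 mg and recurrence means stopping by default. The remaining routes are narrow. The patient must be on 90 mg when the event occurs or have used three reductions from 180 mg, and must then have a separate long interruption. The doses are labelled as recommendations, and dose modifications are discussed at site meetings and reported to the DSMC (Section 10.1.4).

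Much of this stands. The event is rare, a careful investigator would probably keep the patient on 60 mg, and the frequency illustration uses the one route that already carries a ban on escalation. It therefore does not measure the routes where the gap is widest. But none of these points supplies a restart dose. The narrow reading replaces a wrong dose with no dose, and discretion and later reporting do not tell a site what to dispense on the day of restart.

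**Conclusion.** The concern holds. Followed as written, the restart rule gives the wrong dose at one level the protocol itself permits; read narrowly, it gives none. This rests on the text alone: 60 mg is an allowed dose, the rule makes no exception for it, and no other section provides one.

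The size is modest. The 1.5-fold lead-in applies only under the literal reading, the clinical risk of that week cannot be derived from the documents, and the number affected is probably small. Sample size, power and the primary test do not change. This is a minor safety correction that should be made.

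**What to change.** Amend the restart sentence in Section 6.1.2 in two places. After the 90 mg once-daily restart dose, insert *or at the previously tolerated dose if that was lower*. At the end of the sentence, add *if it was above 90 mg*.

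The restart dose becomes min(90 mg, previous dose), and the later step is previous dose − restart dose:

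- previous 60 mg: restart at 60 mg, step 0
- previous 90 mg: restart at 90 mg, step 0
- previous 120 mg: restart at 90 mg, step +30 mg
- previous 180 mg: restart at 90 mg, step +90 mg

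Restarts at 90, 120 and 180 mg are unchanged. The wording adds no new limit on later re-escalation, and the pneumonitis restriction in Section 6.1.2.2 continues to apply to the patients it names.

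The cost is one sentence in an amendment. Section 6.2.2 states, "Brigatinib drug product is supplied as film-coated tablets containing 30 mg of brigatinib active pharmaceutical ingredient", so a 60 mg restart is two tablets of the existing supply. Visits, sample size and analysis are unaffected.

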6.1.2.1 RECOMMENDED BRIGATINIB DOSE REDUCTION LEVELS

Table 1: Recommended Brigatinib Dose Reduction Levels

Starting Dose	Dose Reduction Levels				
	First	Second	Third	Fourth	Fifth
90mg QD	60mg QD	Permanently discontinue	Not applicable	Not applicable	Not applicable
180mg QD	120mg QD	90mg QD	60mg QD	Permanently discontinue	Not applicable

6.1.2.2 DOSE MODIFICATIONS FOR PNEUMONITIS

Pneumonitis and interstitial lung disease are known side effects of TKIs used in NSCLC, generally occurring later in the course of therapy. Crizotinib has been associated with severe, life-threatening, or fatal treatment-related pneumonitis in clinical trials with a frequency of 4 in 255 (1.6%) patients. Other TKIs used in the treatment of NSCLC have similar adverse reactions. In the ALTA trial, brigatinib was associated with pneumonitis in 3.7% of patients in the 90 mg group (90 mg once daily) and 9.1% of patients in the 90 → 180 mg group (180 mg once daily with 7-day lead-in at 90 mg once daily). Adverse reactions consistent with possible ILD/pneumonitis occurred early (within 9 days of initiation of brigatinib; median onset was 2 days) in 6.4% of patients, with Grade 3 to 4 reactions occurring in 2.7%.

Drug-related pneumonitis may be associated with signs and symptoms such as dyspnea, hypoxia, cough, hemoptysis, and fever as well as radiologic evidence of parenchymal or interstitial changes. The diagnosis of pneumonitis and determination of causal relationship to the drug is

often confounded by the underlying disease (especially lymphangitic carcinomatosis) and other factors such as lung infection and radiation effect due to non-specific signs and symptoms as well as similar radiological appearance. Pneumonitis should be suspected when such signs and symptoms develop or in asymptomatic patients when a new ground glass opacity or interstitial infiltration is noted in imaging studies. If a patient is considered to have the potential diagnosis of drug-related pneumonitis, physical examination, assessment of oxygen saturation, evaluation for infectious etiologies, and thoracentesis, bronchoscopy, or open lung biopsy should be considered to reach a diagnosis. If the causality is at least possibly related to the study drug, management of pneumonitis, including dose interruption and potential discontinuation, as presented in during first 7 days of treatment prior to escalation to 180 mg QD) and after escalation to 180 mg QD), is required.

BRIGATINIB DOSE MODIFICATION RECOMMENDATIONS FOR TREATMENT-RELATED PNEUMONITIS OCCURRING PRIOR TO DOSE ESCALATION TO 180 MG QD (IE, FIRST 7 DAYS OF TREATMENT):

Toxicity Grade (CTCAE v4.03)	Recommended Action
Grade 1	Withhold the dose until pneumonitis returns to grade 0 (baseline), then resume at 90 mg and do not escalate. If pneumonitis recurs, permanently discontinue treatment.*
Grade 2	Withhold the dose until pneumonitis returns to Grade 0, then resume at 60 mg and do not escalate.* If pneumonitis recurs, permanently discontinue treatment.*
Grade 3	Permanently discontinue treatment.*
Grade 4	Permanently discontinue treatment.*

*Or in select cases per investigator discretion and discussion with Lead PI, consider continued use/shallower dose escalation as per Camidge et al, JTO 2019

BRIGATINIB DOSE MODIFICATION RECOMMENDATIONS FOR TREATMENT-RELATED PNEUMONITIS OCCURRING AFTER DOSE ESCALATION TO 180 MG QD:

Toxicity Grade (CTCAE v4.03)	Recommended Action
Grade 1	Withhold the dose until pneumonitis returns to grade 0 (baseline), then resume at the same dose. If pneumonitis recurs, permanently discontinue treatment.*
Grade 2	Withhold the dose until pneumonitis returns to Grade 0. Resume at 120 mg QD.* If pneumonitis recurs, permanently discontinue treatment.*
Grade 3	Permanently discontinue treatment.*
Grade 4	Permanently discontinue treatment.*

*Or in select cases per investigator discretion and discussion with Lead PI, consider continued use/shallower dose escalation as per Camidge et al, JTO 2019

6.1.2.3 DOSE MODIFICATION RECOMMENDATION TABLE FOR TREATMENT-RELATED ADVERSE EVENTS (EXCLUDING PNEUMONITIS)

Table 2: Brigatinib Dose Modification Recommendations for Treatment-Related Adverse Events (excluding pneumonitis)

Adverse Reaction	Severity*	Dose Modification
Hypertension	Grade 3 hypertension (SBP greater than or equal to 160 mmHg or DBP greater than or equal to 100 mmHg, medical intervention indicated, more than one anti-hypertensive drug, or more intensive therapy than previously used indicated)	
Withhold brigatinib until hypertension has recovered to Grade 1 or less (SBP less than 140 mmHg and DBP less than 90 mmHg), then resume brigatinib at same dose.Recurrence: withhold brigatinib until recovery to Grade 1 or less, and resume at next lower dose (Table 1) or permanently discontinue treatment.
	Grade 4 hypertension (life-threatening consequences, urgent intervention indicated)	
Withhold brigatinib until recovery to Grade 1 or less (SBP less than 140 mmHg and DBP less than 90 mmHg), and resume at next lower dose (Table 1) or permanently discontinue treatment.Recurrence of Grade 4 hypertension: permanently discontinue brigatinib.
Bradycardia (HR less than 60 bpm)	Symptomatic bradycardia	
Withhold brigatinib until recovery to asymptomatic bradycardia or to a resting heart rate of 60 bpm or above.If a concomitant medication known to cause bradycardia is identified and

Adverse Reaction	Severity*	Dose Modification
		
discontinued or dose-adjusted, resume brigatinib at same dose upon recovery to asymptomatic bradycardia or to resting heart rate of 60 bpm or above.
 
• If no concomitant medication known to cause bradycardia is identified, or if contributing concomitant medications are not discontinued or dose-adjusted, resume brigatinib at next lower dose (Table 1) upon recovery to asymptomatic bradycardia or to resting heart rate of 60 bpm or above.
	Bradycardia with life-threatening consequences, urgent intervention indicated	
• Permanently discontinue brigatinib if no contributing concomitant medication is identified.• If contributing concomitant medication is identified and discontinued or dose-adjusted, resume brigatinib at next lower dose (Table 1) upon recovery to asymptomatic bradycardia or to a resting heart rate of 60 bpm or above, with frequent monitoring as clinically indicated.• Recurrence: permanently discontinue brigatinib.
Visual Disturbance	Grade 2 or 3 visual disturbance	Withhold brigatinib until recovery to Grade 1 or baseline, then resume at the next lower dose (Table 1)

Adverse Reaction	Severity*	Dose Modification
	Grade 4 visual disturbance	Permanently discontinue brigatinib
Creatine Phosphokinase (CPK) Elevation	Grade 3 CPK elevation (greater than $5.0 \times$ ULN)	
Withhold brigatinib until recovery to Grade 1 or less (less than or equal to $2.5 \times$ ULN) or to baseline, then resume brigatinib at same dose.If Grade 3 elevation of CPK recurs, brigatinib should be withheld until recovery to Grade 1 or less (less than or equal to $2.5 \times$ ULN) or to baseline, then resume at the next lower dose level per Table 1.
	Grade 4 CPK elevation (greater than $10.0 \times$ ULN)	
Withhold brigatinib until recovery to Grade 1 or less (less than or equal to $2.5 \times$ ULN) or to baseline, then resume brigatinib at next lower dose (Table 1).If Grade 4 elevation of CPK recurs, permanently discontinue brigatinib
Lipase/Amylase Elevation	Grade 3 lipase or amylase elevation (greater than $2.0 \times$ ULN)	
Withhold brigatinib until recovery to Grade 1 or less (less than or equal to $1.5 \times$ ULN) or to baseline, then resume brigatinib at same dose.If Grade 3 elevation of lipase and amylase reoccurs, brigatinib should be withheld until recovery to Grade 1 or less (less than or equal to $1.5 \times$ ULN) or to baseline, then resume at the next lower dose level per Table 1.

Adverse Reaction	Severity*	Dose Modification
	Grade 4 lipase or amylase elevation (greater than 5.0 × ULN)	
Withhold brigatinib until recovery to Grade 1 or less (less than or equal to 1.5 × ULN) or to baseline, then resume brigatinib at next lower dose (Table 1).If Grade 4 elevation of lipase/amylase recurs, permanently discontinue brigatinib
Hyperglycemia	Grade 3 (greater than 250 mg/mL or 13.9 mmol/L) or greater	If adequate hyperglycemic control cannot be achieved with optimal medical management, withhold brigatinib until adequate hyperglycemic control is achieved and consider reduction to the next lower dose (Table 1) or permanently discontinue brigatinib..
Other	Grade 3	
Withhold brigatinib until recovery to baseline, then resume at same dose.Recurrence: withhold brigatinib until recovery to baseline, then resume at next lower dose or discontinue brigatinib (Table 1).
	Grade 4	
First occurrence: either withhold brigatinib until recovery to baseline and resume at next lower dose (Table 1) or permanently discontinue.Permanently discontinue brigatinib for recurrence.

bpm = beats per minute; DBP = diastolic blood pressure; HR = heart rate; SBP = systolic blood pressure; ULN = upper limit of normal

Adverse Reaction	Severity*	Dose Modification

*Graded per National Cancer Institute Common Terminology Criteria for Adverse Events Version 4.03 (NCI CTCAE v4).
 
Asymptomatic lab abnormalities may be excluded pending discussion with the lead PI. Hypertension grading should be based on persistent blood pressure readings on optimal therapy, rather than specific drug use for the therapy
		

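### The post-escalation Grade 2 pneumonitis rule restarts every patient at 120 mg, which is no reduction from 120 mg and an increase from 90 or 60 mg

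*Combined protocol and SAP*

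**What the plan says.** Section 6.1.2.2 has two tables for treatment-related pneumonitis, one for the 90 mg lead-in and one for the period after escalation to 180 mg. In the second, the Grade 2 instruction is "Withhold the dose until pneumonitis returns to Grade 0. Resume at 120 mg QD", and recurrence means permanent discontinuation. The Grade 1 row of the same table is relative to the current dose: after recovery, "then resume at the same dose. If pneumonitis recurs, permanently discontinue treatment". In the lead-in table, Grade 2 patients recover and "then resume at 60 mg and do not escalate".

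Table 1 in section 6.1.2.1 gives the ladder for patients who started on 180 mg: "180mg QD 120mg QD 90mg QD 60mg QD Permanently discontinue". Table 2 in section 6.1.2.3 moves patients down that ladder one level at a time for other toxicities. Its title excludes pneumonitis.

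Section 6.1.2 has a separate rule for breaks of 14 days or more that are not due to adverse reactions: "resume treatment at 90 mg once daily for 7 days before increasing to the previously tolerated dose". For the rest it says: "Interruptions due to treatment related AEs should be managed as per section 6.1.2.2 and 6.1.2.3 below".

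A footnote attached to the pneumonitis actions allows exceptions: "Or in select cases per investigator discretion and discussion with Lead PI, consider continued use/shallower dose escalation", with a reference to a 2019 publication.

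**The concern.** The heading of the second table fixes when the pneumonitis occurs (after escalation), not the dose the patient is taking at the time. A patient can be escalated to 180 mg, reduced under Table 2 for another toxicity, and then have a first Grade 2 pneumonitis at 120, 90 or 60 mg. For that patient a fixed 120 mg restart is either no reduction or an increase.

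This matters for safety rather than for inference. The patient would return after drug-related lung injury to the same or a higher dose. At 90 or 60 mg, the restart would also undo a reduction made for a different toxicity. The protocol's own background suggests that dose is relevant: section 6.1.2.2 reports pneumonitis in 3.7% of patients in the 90 mg group of the earlier brigatinib trial and 9.1% in the 90→180 mg group.

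**Working it through.** **Inputs**

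- Restart dose after post-escalation Grade 2 pneumonitis: 120 mg (section 6.1.2.2).
- Ladder from 180 mg: 120, 90, 60 mg, discontinue (Table 1, section 6.1.2.1).
- Restart dose after post-escalation Grade 1 pneumonitis: the current dose (section 6.1.2.2).

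**Can an escalated patient be below 180 mg at a first pneumonitis?** Yes. One Table 2 event is enough to reach 120 mg. Examples are Grade 2 or 3 visual disturbance, Grade 4 CPK elevation, Grade 4 lipase or amylase elevation, and symptomatic bradycardia with no contributing drug identified and dealt with. Reaching 90 mg takes two reductions and 60 mg takes three. Study treatment can last 24 months.

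**Reproducing the stated dose.** From 180 mg the first Table 1 reduction is 120 mg, so the row is right for a patient still on 180 mg.

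**Applying the fixed dose at every level.** Change = (120 − onset dose) / onset dose.

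| Dose at onset | Grade 2 restart as written | Change | Table 1 next step | Grade 1 restart |
|---|---|---|---|---|
| 180 mg | 120 mg | (120 − 180)/180 = −33.3% | 120 mg | 180 mg |
| 120 mg | 120 mg | (120 − 120)/120 = 0% | 90 mg | 120 mg |
| 90 mg | 120 mg | (120 − 90)/90 = +33.3% | 60 mg | 90 mg |
| 60 mg | 120 mg | (120 − 60)/60 = +100% | discontinue | 60 mg |

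The row agrees with Table 1 at one of the four levels. Relative to the ladder, the restart is 120/90 = 1.33 times the Table 1 dose for onset at 120 mg and 120/60 = 2 times for onset at 90 mg. For onset at 60 mg the ladder allows no restart. The last column shows the order of severity failing: Grade 2 is handled no more cautiously than Grade 1 at 120 mg, and with a higher restart dose at 90 and 60 mg.

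**Does another rule cap the restart?**

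- The return to a previously tolerated dose in section 6.1.2 covers only interruptions not due to adverse reactions. The same section sends treatment-related interruptions back to 6.1.2.2 and 6.1.2.3.
- Table 2 excludes pneumonitis, so its next-lower-dose rules do not apply.
- The footnote relaxes the rule for selected cases. As worded in the protocol, it does not hold the restart at or below the dose at onset.

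**The case against.** The strongest reply is that the row simply names the first step down from the nominal dose of 180 mg, and that nobody meant it to reverse an earlier reduction. That may well be the intent. On that reading, however, the protocol has no Grade 2 rule for a patient already reduced, and Table 2 cannot supply one. The same edit repairs either reading.

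Second, fixed doses are the style of this section: the lead-in rows also name 90 and 60 mg. This is true, and a patient already cut to 60 mg during the lead-in would also get no reduction. The difference is that lead-in patients are normally on 90 mg, so 60 mg is ordinarily a real reduction and never an increase.

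Third, the tables are labelled as recommendations. The introductory text ends "and after escalation to 180 mg QD), is required", but that sentence is garbled, and what it requires is management including interruption and possible discontinuation; it does not name the restart dose. It is weak support for calling 120 mg mandatory. Section 4.1 also sets the 180 mg dose subject to tolerance, and section 7.2 requires stopping for intolerable toxicity as judged by the investigator. These points make it unlikely that the row would be followed literally in a patient on 90 or 60 mg. None of them states a cap. The publication cited in the footnote was not available, so whatever it specifies for the exception route could not be assessed.

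Fourth, numbers. Applying the cited 9.1% to 23 patients gives 0.091 × 23 ≈ 2.1 pneumonitis cases of any grade. If 30% to 70% of these were Grade 2 and 10% to 50% of those patients had already been reduced (both ranges are assumptions), the expected number affected is 2.1 × 0.30 × 0.10 ≈ 0.06 to 2.1 × 0.70 × 0.50 ≈ 0.7. It would be lower still at 90 or 60 mg. The early onset that section 6.1.2.2 describes (6.4% within 9 days) pushes this down further, although the same section says that TKI pneumonitis generally comes later. This part of the objection stands: few patients, if any, would be affected.

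**Conclusion.** The row is wrong as written for any escalated patient already below 180 mg: 0% change from 120 mg, +33% from 90 mg and +100% from 60 mg, where the protocol's own ladder gives 90 mg, 60 mg and discontinuation. The result rests on reading the table heading as describing timing, which is what it says; the Grade 1 row beside it works at every dose level. Under the narrower reading, the defect becomes a missing rule for the same patients.

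The practical risk is limited by withholding until Grade 0, by discontinuation on recurrence, by investigator discretion and by small numbers. The documents do not give the number who would be affected. The primary endpoint, sample size and analysis are not involved. It is still worth correcting, because a written instruction can raise the dose after a Grade 2 lung toxicity and three sites have to apply it consistently.

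**What to change.** In the post-escalation table, replace the fixed 120 mg in the Grade 2 row with: *Resume at the next lower dose (Table 1); permanently discontinue if pneumonitis occurred at 60 mg QD.* Keep the withholding to Grade 0, the recurrence rule and the footnote. The restarts become 180→120 mg (unchanged), 120→90 mg, 90→60 mg, and discontinuation from 60 mg.

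The cost is the wording of one table row in an amendment. The edit uses a convention that Table 2 already follows and leaves the endpoint, sample size and analysis unchanged.
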